#### **4.3.6.7. BMI Z-Score Reduction in Patients Aged $\geq 4$ to <18 Years**

The proportion of pivotal and all patients aged  $\geq 4$  to <18 years achieving a  $\geq 0.2$ -point reduction of BMI Z-score from baseline will be analyzed for the mITT. Binomial proportions will be calculated for each treatment arm for each of the 100 imputed datasets. Analysis between arms will be conducted for each of the 100 imputed datasets with a CMH test with adjustment of stratification factors of age group ( $\geq 12$  and <18 years old, <12 years old) and subpopulation (Japanese and non-Japanese), as appropriate. This analysis will follow the same methodology as the first key secondary efficacy endpoint as outlined in [Section 4.3.5.1](#).

#### **4.3.6.8. Proportion of Patients with BMI <30 kg/m^2 ( $\geq 18$ years) or <95th percentile (<18 years)**

For consistency with BMI percent of 95th percentile analyses, a subject's 95th BMI percentile will be based upon the CDC macro as outlined in [Section 4.3.6.6](#) and is age and sex dependent.

The proportion of patients with BMI <30 kg/m^2 (patients aged  $\geq 18$  years) or <95th percentile (patients aged <18 years) after approximately 52 weeks will be analyzed. Binomial proportions will be calculated for each treatment arm for each of the 100 imputed datasets. Analysis between arms will be conducted for each of the 100 imputed datasets with a CMH test with adjustment of stratification factors of age group ( $\geq 12$  and <18 years old, <12 years old) and subpopulation (Japanese and non-Japanese), as appropriate. This analysis will follow the same methodology as the first key secondary efficacy endpoint outlined in [Section 4.3.5.1](#).

Patient BMI percentiles will be included on the BMI percent of 95th percentile by-patient listing.

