The between-group comparison on the two-sample proportions in the above No. 1, 3, 4, 7, and 8 endpoints will be conducted with a Cochran–Mantel–Haenszel (CMH) test with adjustment of stratification factors of age group and subpopulation (Japanese and non-Japanese) at a 2-sided 0.05 significance level. The associated corresponding 2-sided 95% CI will be presented. The analysis will be based on the mITT population.

The between-group comparison on the two-sample means in the above number 2, 5, 6, 9, 10 and 11 endpoints will be conducted with ANCOVA models. The statistical hypothesis will be tested at a 2-sided 0.05 significance level. A 2-sided 95% CI will be calculated and presented.

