1.3.2. Randomization Methodology

Patients who are eligible to enter the trial will be randomized in a blinded manner on Day 1 in a 2:1 ratio (setmelanotide:placebo), stratified by age group ( $\geq 18$  years old,  $\geq 12$  and  $< 18$  years old,  $< 12$  years old) and subpopulation (Japanese vs non-Japanese), to receive either setmelanotide or placebo. The randomization schedule will be generated by the Sponsor or its designee, and trial personnel will use a web-based interactive response technology (IRT) system to obtain the patient number for each eligible patient.

The patient, Investigator, and the Sponsor will be blinded to trial treatment assignment. Full details for the blinding and unblinding are provided in the separate Blinding and Unblinding Plans.

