4.2. Demographics and Baseline Characteristics

Demographics and baseline characteristics information will be summarized by treatment group and overall. Age, height, weight, waist circumference, BMI, BMI P95, and BMI Z-Score at baseline will be summarized using descriptive statistics, as applicable. The number and percentage of participants in each age group (<12 years old, ≥12 to <18 years old, ≥18 years old), sex, ethnicity, race, and subpopulation (Japanese vs non-Japanese) will also be presented. Skin type as measured by the Fitzpatrick Classification Scale as defined in Table 4-1, will also be summarized. Patient demographics and baseline characteristics will be summarized for the mITT for pivotal patients and all patients. A separate summary of patient demographics and baseline characteristics will be provided for Japanese patients only.

Table 4-1 Fitzpatrick Classification Scale

Skin Type	Skin Color	Characteristics
I	White; very fair; red or blond hair; blue eyes; freckles	Always burns, never tans
II	White; fair; red or blond hair; blue, hazel, or green eyes	Usually burns, tans with difficulty
III	Cream white; fair with any eye or hair color; very common	Sometimes mild burn, gradually tans
IV	Brown; typical Mediterranean Caucasian skin	Rarely burns, tans with ease
V	Dark Brown; mid-eastern skin types	Very rarely burns, tans very easily
VI	Black	Never burns, tans very easily

Source: [Fitzpatrick 1975](#)

Patient demographic and baseline characteristics data will be provided in by-patient listings.

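### SAP 4.3.6.8 lists only the two paediatric age strata for an endpoint that includes adults, so adults have no stratum in the CMH comparison as written

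*SAP*

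**What the plan says.** SAP 4.3.6.8 sets one response criterion for each side of age 18. For adults it is BMI below 30 kg/m²; for the rest it is a position below the 95th "percentile (patients aged <18 years) after approximately 52 weeks will be analyzed".

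The comparison between arms is a CMH test in each of the 100 imputed datasets. The age factor is spelled out in brackets. It names the band from 12 up to 18, then continues: "and <18 years old, <12 years old) and subpopulation (Japanese and non-Japanese), as appropriate". No band for 18 and over is given.

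The paragraph closes with a cross-reference to SAP 4.3.5.1: "This analysis will follow the same methodology as the first key secondary efficacy endpoint outlined in" that section. SAP 4.3.5.1 takes an adjusted risk difference over all strata from PROC FREQ, with its confidence interval, and pools it with PROC MIANALYZE. It also pools the responder proportion in each arm.

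Protocol 7.5.2 lists this endpoint as No. 8 and groups it with the other proportions: "The between-group comparison on the two-sample proportions in the above No. 1, 3, 4, 7, and 8 endpoints will be conducted" with a CMH "test with adjustment of stratification factors of age group and subpopulation (Japanese and non-Japanese) at a 2-sided 0.05 significance level". Nothing there limits the age factor to children.

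**The concern.** The age levels listed for the test do not cover the patients for whom the endpoint is defined. A stratified CMH analysis uses only patients who have a value on every stratification variable. If the age variable is built from the bracketed list, adults have no value and contribute nothing to the common risk difference, its interval or its p-value.

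Two things are at stake. First, the adult half of the endpoint, leaving the obese range, would not inform the treatment comparison. Second, the output could mislead. The responder proportions by arm need no strata, so they could be computed on all ages and printed beside a risk difference and p-value that rest on children alone, under a heading that names both groups.

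**Working it through.** The plan states no power or sample size for this endpoint. Its only power figure, about 99.5%, concerns the primary endpoint and does not bear on this point. The check is therefore mainly a comparison of text.

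**1. Age levels listed, against the ages analysed, across the SAP**

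| SAP section | Ages in the endpoint | Age levels listed |
|---|---|---|
| 4.3.2 (primary) | all | ≥18; 12 to <18; <12 |
| 4.3.6.1 (hunger responder) | ≥12 | ≥18; 12 to <18 |
| 4.3.6.7 (Z-score responder) | 4 to <18 | 12 to <18; <12 |
| **4.3.6.8 (this endpoint)** | **all** | **12 to <18; <12** |
| 4.3.6.10 and 4.3.6.11 | all | ≥18; 12 to <18; <12 |

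In each of these sections except 4.3.6.8, the list matches the ages analysed. SAP 3.6 states that practice for ANCOVA models. Section 4.3.6.8 carries the list of the section directly before it, which points to carried-over text.

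**2. Against the design.** SAP 1.3.2 randomizes by three age groups crossed with "years old) and subpopulation (Japanese vs non-Japanese), to receive either setmelanotide or placebo". SAP 4.2 summarises patients "in each age group (<12 years old, ≥12 to <18 years old, ≥18 years old". SAP 4.3.6.3 and 4.3.6.4, responder endpoints for all ages, name the age group without restricting it.

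**3. Strata count**

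- As listed: 2 age levels × 2 subpopulations = 4 strata, all paediatric.
- As randomized: 3 age levels × 2 subpopulations = 6 strata, covering everyone.

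**4. How many patients would be lost.** The documents give no adult share. Let it be s, assumed to lie between 0.30 and 0.60, with N = 120 (80 setmelanotide, 40 placebo). Patients lost = s × 120.

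- s = 0.30: 0.30 × 120 = 36 lost; 84 remain (56 and 28).
- s = 0.60: 0.60 × 120 = 72 lost; 48 remain (32 and 16).

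**5. Effect on precision.** If response rates are similar in adults and children and the 2:1 ratio holds, the standard error of the risk difference grows by 1/√(1 − s).

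- s = 0.30: 1/√0.70 = 1.20.
- s = 0.60: 1/√0.40 = 1.58.

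**6. Illustration of power.** The response rates here, 25% against 5%, are invented to give a sense of scale; the documents supply none. Use power = Φ[(d − 1.96 × SE₀)/SE₁] with d = 0.20. SE₀ is the pooled standard error and SE₁ the unpooled one. Stratification and imputation are ignored.

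- All 120: the pooled rate is (40 × 0.05 + 80 × 0.25)/120 = 0.183. SE₀ = √[0.183 × 0.817 × (1/40 + 1/80)] = 0.0749. SE₁ = √[0.05 × 0.95/40 + 0.25 × 0.75/80] = 0.0594. Power = Φ(0.894) = 81.4%.
- 84 children: both standard errors × 1.195, giving 0.0896 and 0.0710. Power = 63.5%.
- 48 children: both × 1.581, giving 0.1185 and 0.0940. Power = 36.6%.

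Steps 1 to 3 rest on the documents alone. Steps 4 to 6 rest on the stated assumptions.

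**The case against.** The strongest reply is that the paragraph contradicts itself but does not exclude adults. It defines a response for them, it sends the reader to SAP 4.3.5.1, whose endpoint includes adults and whose age factor is not restricted, and unlike SAP 4.3.6.6 and 4.3.6.7 it never limits the population in words. Age group already exists as a three-level variable for every patient. A programmer who uses it keeps the adults in, and they drop out only if someone builds a new two-level variable from the brackets. A mismatch between arm proportions and risk difference might also be noticed.

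Much of this stands as a reading of intent: adults were plainly meant to be analysed. It does not repair the rule. SAP 4.3.5.1 says only age group, so the bracketed list in 4.3.6.8 is the more specific instruction, and a programmer must either follow it or depart from the SAP. The words allowing adjustment where suitable also appear in correctly specified sections and cannot supply a missing level. A possible mismatch in the output is no safeguard, since nothing in the plan calls for that check.

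Three further points are fair. The adult share and the response rates are assumptions. The levels are not spelled out in SAP 4.3.5.1, so a correction should point to SAP 1.3.2 and 4.3.2. And this is one of 11 other secondary endpoints, outside the fixed sequence.

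**Conclusion.** The concern holds. The age levels in SAP 4.3.6.8 contradict the endpoint defined in the same paragraph, the randomization strata and the analysis in Protocol 7.5.2. No passage assigns adults to a stratum or gives a reason for omitting them. Applied as listed, the test uses four paediatric strata where six are needed, and the comparison loses every adult.

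The size depends on the age mix. On an assumed adult share of 30% to 60%, that is 36 to 72 of 120 patients, with a standard error about 1.2 to 1.6 times as large. The larger issue is that the estimate would describe children only. The trial's success conclusion and the three key secondary endpoints are not affected. It should be corrected, and it ranks well below anything touching the primary analysis.

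**What to change.** In SAP 4.3.6.8, replace the bracketed age levels with the three used for randomization (≥18; ≥12 and <18; <12), crossed with Japanese and non-Japanese status, citing SAP 1.3.2 and 4.3.2 for the levels. Keep the existing allowance for adapting the adjustment, because SAP 3.12.1 expects the 12 Japanese patients not to be enrolled within the first 120 dosed, so Japanese cells may be sparse in the pivotal cohort.

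The cost is one phrase in the SAP. The protocol needs no amendment, since its wording for this endpoint is already unrestricted. Making the change before unblinding avoids a later choice about which patients count in the comparison.

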#### 4.3.6.9. Quality of Life

Quality of life will be assessed using the Impact of Weight on Quality of Life-Lite-Clinical Trials questionnaires (IWQOL-Lite-CT or IWQOL-Kids).

The IWQOL-Lite-CT will be administered to patients  $\geq 18$  years of age. The IWQOL-Lite-CT is a validated 20-item self-report measure of obesity-specific quality of life questionnaire. The IWQOL-Lite-CT yields a Total score and 3 composite scores: Physical (7 items), Physical Function (5 items), and Psychosocial (13 items).

Mean change in physical functioning score and total score for the IWQOL (IWQOL-Lite-CT in pivotal and all patients  $\geq 18$  years in mITT), from baseline will be analyzed with an ANCOVA model adjusted for baseline score and subpopulation (Japanese and non-Japanese), as appropriate.

The IWQOL-Kids will be administered to patients between the ages of 11 and  $<18$ . The IWQOL-Kids is a validated 27-item self-report measure of weight-related quality of life for youth. It provides a total score inclusive of 4 domains: physical comfort, body esteem, social life, and family relations.

Mean change in total score for the IWQOL-Kids in pivotal and all patients between the ages of 11 and  $<18$  in the mITT will be analyzed with an ANCOVA model adjusted for baseline score and subpopulations (Japanese and non-Japanese), as appropriate.

Descriptive summaries will be presented for both the IWQOL and IWQOL-Kids actual and change from baseline by visit for pivotal and all patients of relevant age in the mITT, as needed.

By-patient listings will be provided for IWQOL-Lite-CT and IWQOL-Kids.

#### 4.3.6.10. Waist Circumference

Change in waist circumference from Baseline after approximately 52 weeks on a therapeutic regimen of setmelanotide compared to placebo will be analyzed.

The between-group comparison will be conducted for pivotal and all patients in the mITT using an ANCOVA model adjusted with baseline measurement and a stratification factor of age groups ( $<12$  years old,  $\geq 12$  and  $<18$  years old, and  $\geq 18$  years old) and subpopulations (Japanese and non-Japanese), as appropriate.

The actual, change from baseline, and percent change from baseline for waist circumference will be summarized descriptively by visit for pivotal and all patients in the mITT, as needed.

Change from baseline in waist circumference will be presented graphically by treatment group and visit, with standard error bars included, for the mITT for pivotal and all patients. The x-axis will include visit in weeks and the y-axis will represent the observed mean  $\pm$  SE of percent change from baseline.

By-patient listing will be provided based on reported results.

4.3.6.11. Cardiometabolic Parameters

The difference in change in cardiometabolic parameters including blood pressure, CCI liver function and CCI from Baseline after approximately 52 weeks on a therapeutic regimen of setmelanotide compared to placebo will be analyzed.

Mean change in each cardiometabolic parameter from baseline will be analyzed for pivotal and all patients in the mITT with an ANCOVA model adjusted with baseline measurement and stratification factors of age group ( $\geq 18$  years old,  $\geq 12$  and  $< 18$  years old,  $< 12$  years old) and subpopulation (Japanese and non-Japanese), as appropriate.

The actual, change from baseline, and percent change from baseline for each cardiometabolic parameter will be summarized descriptively by visit for pivotal and all patients in the mITT, as needed.

A by-patient listing will be provided for each cardiometabolic parameter based on reported results.

4.3.7. Exploratory Efficacy Endpoints

4.3.7.1. CCI

[Redacted text block]

[Redacted text block]

[Redacted text block]

[Redacted text block]

4.3.7.2. CCI

[Redacted text block]

[Redacted text block]

[Redacted text block]

CCI [REDACTED]  
[REDACTED]  
[REDACTED]  
[REDACTED]  
[REDACTED]

[REDACTED]  
[REDACTED]

[REDACTED]  
[REDACTED]

4.3.7.3. CCI [REDACTED]

[REDACTED]  
[REDACTED]  
[REDACTED]  
[REDACTED]  
[REDACTED]  
[REDACTED]

[REDACTED]  
[REDACTED]  
[REDACTED]  
[REDACTED]  
[REDACTED]  
[REDACTED]  
[REDACTED]  
[REDACTED]

[REDACTED]  
[REDACTED]  
[REDACTED]  
[REDACTED]

[REDACTED]  
[REDACTED]  
[REDACTED]  
[REDACTED]  
[REDACTED]

[REDACTED]  
[REDACTED]  
[REDACTED]

[REDACTED]  
[REDACTED]  
[REDACTED]

4.3.7.4. CCI

CCI

4.3.7.5. CCI

CCI

4.3.7.6. CCI

CCI

CCI  
[REDACTED]

#### 4.4. Pharmacokinetic Evaluations

PK analysis will be conducted by the Sponsor designee and analysis will be specified in a separate PKAP. However, PK concentration listings will be provided based on the mITT where relevant profile are obtained.

#### 4.5. Safety Analysis

Safety analyses will be conducted using the SA Set.

##### 4.5.1. Drug Exposure

Drug exposure will be summarized for pivotal and all patients by treatment group across the entire length of the study. The number of doses administered, total dose received in mg, treatment duration in weeks, and percentage of dosing compliance will be summarized using descriptive statistics (N, mean, SD, median, minimum, maximum, and 95% confidence intervals). A separate summary for Japanese patients will be provided.

Treatment duration will be defined in weeks as  $(\text{date of last dose} - \text{date of first dose} + 1) / 7$ .

Dosing compliance percentage will be defined as  $(\text{number of doses administered} / \text{the duration of treatment in days}) * 100$ .

A by-patient listing for dosing will be provided.

##### 4.5.2. Adverse Events

All AEs will be coded using the MedDRA coding system (Version 24.0 or later) and displayed in tables by treatment received and in data listings using system organ class and preferred term. AE grade assessment will be based on investigator reporting using the National Cancer Institute Common Terminology Criteria for Adverse Events (NCI-CTCAE), Version 5.0.

Analyses of AEs will focus on those events that are considered treatment-emergent, where treatment-emergent is defined as any AE with onset after the administration of study medication through the end of the study (14 days after last dose administered), any event that was present at

baseline but worsened in intensity or was subsequently considered drug-related by the Investigator through the end of the study, or any event deemed to be related to study drug exposure.

The number and percentage of pivotal and all patients with any treatment-emergent AE (TEAE), with any TEAE assessed by the Investigator as related to treatment (definite, probable, or possible relationship), with any serious TEAE, with any serious related TEAE, with any TEAE leading to study drug withdrawal, or with any TEAE leading to death will be summarized by treatment received, as needed. The aforementioned summaries will be repeated for Japanese patients, as needed.

The number and percentage of pivotal and all patients with treatment-related TEAEs leading to study discontinuation and non-serious TEAEs will also be summarized by treatment received, as needed.

TEAEs of special interest (Nausea, Vomiting, Diarrhea) will be identified and summarized by treatment received for pivotal and all patients, as needed. A separate summary will be provided for Japanese patients.

In these tabulations, each patient will contribute only once (i.e., the most related occurrence or the most intense occurrence) to each of the incidence rates in the descriptive analysis, regardless of the number of episodes.

All AEs occurring on-study will be listed in patient data listings. Listings will also be provided for the following: drug product related TEAEs, serious TEAEs, drug product related serious TEAEs, TEAEs leading to study drug withdrawal, events of special interest, and deaths.

#### **4.5.3. Columbia Suicide Severity Rating Scale (C-SSRS)**

The C-SSRS will be measured as shown in the SoA (Table 1-1) according to the age of the patient (child <12 or adult ≥12). Results of the C-SSRS will be provided in a shift table for pivotal and all patients assessing shifts from the baseline most severe ideation to most severe ideation during follow-up, as needed.

A by-patient listing including the ideation, intensity of ideation, behavior, and number of attempts will be provided.

#### **4.5.4. Patient Health Questionnaire (PHQ-9 or PHQ-A)**

The PHQ-9 is a 9-item depression scale of the Patient Health Questionnaire used to assist clinicians in diagnosing depression as well as selecting and monitoring treatment and is administered to patients ≥18 years old. The PHQ-A is a modification of the PHQ-9 for adolescents (patients ages 11 to 17 years old). Each question has a score from 0 to 3, and all 9 scores are added to produce a total score.

The Patient Health Questionnaire-9 and PHQ-A will be measured as shown in the SoA (Table 1-1). The actual values and change from baseline of the total scores will be summarized with descriptive statistics by visit for pivotal and all patients, as needed.

A by-patient listing of the results of the individual 9 questions will be provided.

#### 4.5.5. Children's Depression Inventory-2 (CDI-2)

The CDI-2 has both a self-report and a parent version. The CDI-2: Self-Report Short version is an efficient screening measure that contains 12 items. The self-report short version will be administered to patients 7 to <12 years of age according to the SoA (Table 1-1).

Items on the CDI-2 Parent form correspond to items on the self-report version and are suitably rephrased. Item selection for the parent forms was guided to maximize validity, and thus focused on observable manifestations of depression. The CDI-2 parent form consists of 17 items and the 4 choices provided for each item correspond to 4 levels of symptomatology: 0 (not at all), 1 (some of the time), 2 (often), or 3 (most of the time). The CDI-2 parent version will be administered to caregivers of patients 7 to <12 years of age according to the SoA (Table 1-1).

The actual values and change from baseline of the total scores will be summarized with descriptive statistics by visit for pivotal and all patients, as needed.

By-patient listings will be provided for each version of the CDI-2.

#### 4.5.6. Global Hunger Questions

The Global Hunger Questions for Patients  $\geq 12$  Years of Age consist of two parts: the Patient Global Impression of Severity (PGIS) and the Patient Global Impression of Change (PGIC).

The Caregiver Global Impression of Severity (CGIS) and the Caregiver Global Impression of Change (CGIC) and will be administered to caregivers of patients <12 years of age or to caregivers of patients who are unable to self-report. PGIS/CGIS only is administered at baseline. Both parts (PGIS/PGIC and CGIS/CGIC) are administered thereafter per the SoA (Table 1-1).

The actual values and change from baseline of the total scores will be summarized with descriptive statistics by visit for pivotal and all patients, as needed. Shift tables will also be provided for pivotal and all patients for each version of the questionnaire, capturing shifts from baseline to each on study visit, as needed.

A by-patient listing of the results questions will be provided.

#### 4.5.7. Thyroxine (T4), Free Thyroxine (T4), and T3

T4, Free T4, and T3 will be measured as shown in the SoA (Table 1-1).

A by-patient listing of the results of will be provided.

